2.6. Efficacy, Pharmacokinetic, Safety and Tolerability Endpoints

2.6.1 Efficacy Endpoints

Primary Efficacy Endpoint

The primary efficacy endpoint is the change from baseline in the weekly CSBM rate during the Fixed Dose period.

Baseline is defined as the weekly CSBM rate during the 2-week screening period. If a subject has more than two weeks of entries during the screening period, consecutive missing entries during the screening period will be excluded from baseline calculations, and the last fourteen days with entries during the screening period will be used to derive baseline weekly rates.

Subjects with fewer than 11 days of diary data during screening would be excluded from the study. The primary efficacy endpoint will be obtained as the weekly CSBM rate during the Fixed Dose period with exceptions as noted in section 4.7. The frequency of CSBMs will be

determined via a web-based electronic diary where the passage of a bowel movement or absence thereof will be recorded daily throughout the study by the subject.

2.6.2 Secondary Efficacy Endpoints

The secondary efficacy endpoints include:

- Frequency of dose adjustments in the Dose Adjustment period: The number of dose adjustments a subject has from the initial starting dose to the subject's fixed dose.
- Prokinetic bowel response during the Fixed Dose period: A prokinetic response is defined as a weekly CSBM rate increase of 1 or more compared to baseline or an absolute rate of 3 or more CSBMs per week.
- Change from baseline in the weekly SBM rate during the Fixed Dose period: An SBM is a bowel movement which did not occur within 24 hours after taking rescue medication.
- SBM bowel response to ENT-01 during the Fixed Dose period: An SBM bowel response is defined as a weekly SBM rate increase of 1 or more compared to baseline or an absolute rate of 3 or more SBMs per week.
- Change from baseline in stool ease of passage during the Fixed Dose period: Stool ease of passage is rated on a 1-7 ordinal point scale (see [APPENDIX 4](#) of the Protocol). A subject's ease of passage score for a given time period is the average of the ease of passage scores associated with SBMs during that time period.
- Change from baseline in stool consistency during the Fixed Dose period: Stool consistency is measured using the 7-point Bristol Stool Chart (see [APPENDIX 5](#) of the Protocol). A subject's stool consistency score for a given time period is the average of the stool consistency scores associated with SBMs during that time period.
- Change from baseline in suppository/enema use during the Fixed Dose period: Suppository/enema use is measured as a weekly average during the Fixed Dose period. This is captured in the subject stool diary.
- Time to first CSBM in the Fixed Dose period: Time to first CSBM in the Fixed Dose period is defined as the time from the subject taking the first dose of study medication in the Fixed Dose period until the subject has a CSBM.
- Time to first SBM in the Fixed Dose period: Time to first SBM in the Fixed Dose period is defined as the time from the subject taking the first dose of study medication in the Fixed Dose period until the subject has an SBM.
- Time to first rescue medication use in the Fixed Dose period: Time to first rescue medication use in the Fixed Dose period is defined as the time from the subject taking the first dose of study medication in the Fixed Dose period until the subject first uses rescue medication.
- Stool-related subjective assessments using the PAC-SYM: Subjective bowel function data is captured using the Patient Assessment of Constipation-Symptoms: The PAC-SYM is a 12-item questionnaire, and each question has a 0 (Absent) – 4 (Very Severe) point response scale. The PAC-SYM overall score is the score obtained by averaging the response from the 12 items. The PAC-SYM scores and change from baseline will be calculated for each scheduled assessment time-point.

- Stool-related subjective assessments using the PAC-QOL: Constipation-related quality of life is assessed using the Patient Assessment of Constipation-Quality of Life. The PAC-QOL is a 28-item questionnaire, and each question has a 5-point ordinal response scale. The PAC-QOL endpoints consist of an overall average score and the four subscale scores (i.e., physical discomfort, psychosocial discomfort, worries/concerns, and satisfaction). The PAC-QOL scores and change from baseline will be calculated for each scheduled assessment time-point.

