3.2 Secondary Objectives and Endpoints

The secondary objectives of the study are:

1. To determine if the correct starting dose (75 mg or 150 mg) can be predicted from the baseline weekly CSBM rate
2. To collect information on the effect of ENT-01 on CSBM, SBM, ease of passage,

consistency, suppository/enema use and subjective bowel function and quality of life (QOL)

Secondary efficacy endpoints will include the following:

- Frequency of dose adjustments in the Dose Adjustment period: The number of dose adjustments a subject has from the initial starting dose to the subject's fixed dose.
- Prokinetic bowel response during the Fixed Dose period: A prokinetic response is defined as a weekly CSBM rate increase of 1 or more compared to baseline or an absolute rate of 3 or more CSBMs per week.
- Change from baseline in the weekly SBM rate during the Fixed Dose period: An SBM is a bowel movement which did not occur within 24 hours after taking rescue medication.
- SBM bowel response to ENT-01 during the Fixed Dose period: An SBM bowel response is defined as a weekly SBM rate increase of 1 or more compared to baseline or an absolute rate of 3 or more SBMs per week.
- Change from baseline in stool ease of passage during the Fixed Dose period: Stool ease of passage is rated on a 1-7 ordinal point scale (see [APPENDIX 5](#)). A subject's ease of passage score for a given time period is the average of the ease of passage scores associated with SBMs during that time period.
- Change from baseline in stool consistency during the Fixed Dose period: Stool consistency is measured using the 7-point Bristol Stool Chart (see [APPENDIX 6](#)). A subject's stool consistency score for a given time period is the average of the stool consistency scores associated with SBMs during that time period.
- Change from baseline in suppository/enema use during the Fixed Dose period: Suppository/enema use is measured as a weekly average during the Fixed Dose period. This is captured in the subject stool diary.
- Time to first CSBM in the Fixed Dose period: Time to first CSBM in the Fixed Dose period is defined as the time from the subject taking the first dose of study medication in the Fixed Dose period until the subject has aCSBM.

- Time to first SBM in the Fixed Dose period: Time to first SBM in the Fixed Dose period is defined as the time from the subject taking the first dose of study medication in the Fixed Dose period until the subject has an SBM.

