5.3 Inclusion Criteria

The study population is defined as subjects who meet the following criteria:

1. Subjects aged 30-90 years, both genders
2. Subjects must provide written informed consent and be willing and able to comply with study procedures.
3. Subjects must be diagnosed with Parkinson's Disease defined as the presence of at least three of the following cardinal features, in the absence of alternative explanations or atypical features: rest tremor, rigidity, bradykinesia and/or akinesia, postural and gait abnormalities.
4. There are insufficient criteria for Irritable Bowel Syndrome (IBS)

5. Constipation which has been present for approximately 6 months
6. Body mass index (BMI) of 18-40 kg/m²
7. Subjects must fulfill Rome IV criteria for functional constipation which includes 2 or more of the following:
 - a. Straining during at least 25% of defecations
 - b. Lumpy or hard stools in at least 25% of defecations
 - c. Sensation of incomplete evacuation for at least 25% of defecations
 - d. Sensation of anorectal obstruction/blockage for at least 25% of defecations
 - e. Manual maneuvers to facilitate at least 25% of defecations (e.g., digital evacuation, support of the pelvic floor)
8. Self-report of 3 or fewer complete spontaneous bowel movements (CSBMs) per week
9. Loose stools are rarely present without the use of laxatives
10. Subjects must be able to read, understand, and accurately record data into the diary to guarantee full participation in the study.
11. Female subjects must have negative serum or urine pregnancy tests and must not be lactating. For females able to bear children, hormonal (i.e., oral, implantable, or injectable), abstinence, same sex relationships, single-barrier method, or a double-barrier method of birth control must be used throughout the study. A vasectomized partner will be allowed as one in conjunction with another single-barrier method.
12. Female subjects unable to bear children must have this documented in the CRF (i.e., tubal ligation, hysterectomy, or postmenopausal [defined as a minimum of one year since the last menstrual period]). Post-menopausal status will be confirmed by follicle stimulating hormone (FSH) in women less than 60 years of age

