5.4 Exclusion Criteria

1. Unable or unwilling to provide informed consent or to comply with study procedures.
2. Diagnosis of secondary constipation beyond that of Parkinson's Disease

3. Review of Screening Diaries indicates either of the following:

- Fewer than 11 days of diary completion and/or
- More than 3 complete spontaneous bowel movements per week based upon the average CSBM rate reported during the Screening Period.

4. A compromised gastrointestinal system which includes:

- Structural, metabolic, or functional GI diseases or disorders
- Acute GI illness within 2 weeks of the screening visit
- History of major GI surgery within 30 days of the screening visit (a history of cholecystectomy, polypectomy, hernia repair or appendectomy are not exclusionary as long as they were performed more than 30 days before the screening visit)

5. Unable or unwilling to withdraw from laxatives, opiates, clonazepam, or any medications which may cause constipation, 2 weeks prior to the dose adjustment period and throughout the rest of the study.

6. Unable or unwilling to withdraw from proton pump inhibitors and antacids at the end of the screening period.

7. Any clinically significant abnormalities on screening laboratories or physical examination requiring further evaluation or treatment.

8. Neurological disorder other than Parkinson's Disease that in the opinion of the investigator might interfere with the conduct of the study.

9. On treatment with intra-jejunal dopamine or carbidopa/levodopa (i.e. Duopa).

10. Subjects starting a new Parkinson's Disease medication or modifying an existing medication within 2 weeks prior to enrollment.

11. Unable to maintain a stable diet regimen.

12. Subjects with a cognitive impairment that preclude them from understanding the informed consent.

13. Subjects placed under legal guardianship.

14. Females who are pregnant or breastfeeding.
15. History of excessive alcohol use or substance abuse.
16. Participation in an investigational drug trial within the month prior to dosing in the present study.
17. Any other reason, which, in the opinion of the investigator, would confound proper interpretation of the study.

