2.4. Study Procedures

The schedule of events, as outlined in the study protocol, is provided in Table 1.

Table 1. Schedule of Events

	Visit 1 Screening	Visit 2 Randomization	Visit 3 Follow-Up	Visit 4 End of Treatment	Visit 5 End of Placebo	Visit 6 End of Study	Early Termination
	Day -14	Day 1 (+/- 2days)	Day 11 (+/- 1day)	Day 26 (- 2 days)	Day 39 (+/- 2days)	Day 69 (+/- 3 days)	
Informed Consent	X						
Inclusion/Exclusion Criteria ^a	X	X					
Demographics/Medical History	X						
Complete Physical Exam	X						X
Brief Physical Exam			X	X	X	X	
Height	X						
Weight	X	X	X	X	X	X	X
Orthostatic Vital Signs ^b	X	X	X	X	X	X	X
12-lead ECG	X	X	X	X	X	X	X
Labs and Urinalysis	X		X	X	X	X	X
Pregnancy Testing ^c	X	X	X	X	X	X	X
In-clinic IP/Placebo Dosing ^d			X	X	X		
In-clinic Levodopa Dosing		X	X	X	X	X	X
Levodopa PK Draws ^e		X	X	X	X	X	X
IP/Placebo Dispense		X	X	X			
IP/Placebo Collection and Accountability			X	X	X	X	X

	Visit 1 Screening	Visit 2 Randomization	Visit 3 Follow-Up	Visit 4 End of Treatment	Visit 5 End of Placebo	Visit 6 End of Study	Early Termination
	Day -14	Day 1 (+/- 2 days)	Day 11 (+/- 1 day)	Day 26 (- 2 days)	Day 39 (+/- 2 days)	Day 69 (+/- 3 days)	
Instructions to Discontinue Laxatives and other BM Medications	X						
Dispense Rescue Medications ^f	X	X	X	X	X		
Stool Diary Instruction/Review ^g	X	X	X	X	X	X	X
AE Review	X	X	X	X	X	X	X
Prior and Con Meds	X	X	X	X	X	X	X
Rome IV questionnaire	X						
MDS-UPDRS ^h	X		X	X	X	X	X
C-SSRS	X	X	X	X	X	X	X
BDI-II	X		X	X	X	X	X
MMSE	X		X	X	X	X	X
SAPS-PD, Hallucination/Delusion Questionnaire ⁱ	X	X	X	X	X	X	X
PAC-QOL and PAC-SYM		X	X	X	X	X	X
Dispense Stool Collection Kits	X		X				
Collect Stool Sample ^j		X		X			

a. Confirmation of eligibility: To be randomized to receive double-blind study medication in this study, subjects must meet the following criteria:

- Have had at least 11 “Available Data Days” (days with electronic diary compliance sufficient for determining whether a BM occurred)
- Have had <3 CSBMs/week based upon the average CSBM rate during the first 2 screening weeks (baseline period).
- Be approved for randomization by the enrollment committee

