2.6.3 Exploratory efficacy endpoints

The exploratory efficacy endpoints include:

- A weekly CSBM rate increase of 1 or more compared to baseline and an absolute rate of 3 or more CSBMs per week in the Fixed Dose period (i.e., this is a modification of the Prokinetic Response secondary endpoint using “AND” instead of “OR” as the criterion).
- A weekly SBM rate increase of 1 or more compared to baseline and an absolute rate of 3 or more CSBMs per week in the Fixed Dose period.
- Change from baseline in the weekly CSBM rate during the Placebo Withdrawal and Washout periods.
- Change from baseline in the weekly SBM rate during the Placebo Withdrawal and Washout periods.
- Change from baseline in stool ease of passage during the Placebo Withdrawal and Washout periods.
- Change from baseline in stool consistency during the Placebo Withdrawal and Washout periods.
- Change from baseline in suppository/enema use during Placebo Withdrawal and Washout periods.
- Improvement in frequency and/or severity of hallucinations/delusions during the Fixed Dose period over baseline: Improvement is defined as an improvement of 2.33 points or greater reduction in score from baseline on the Scale for the Assessment of Positive Symptoms -Parkinson's Disease (SAPS-PD). Up to 40% of subjects are expected to have minor or major hallucinations and/or delusions. The SAPS-PD will be administered at Screening, and subsequently will only be administered to those subjects with hallucinations and/or delusions (as determined by an SAPS-PD score >0 at the Screening visit).
- Improvement of the symptoms of Parkinson's Disease as assessed by the UPDRS: The standard four-part UPDRS will be administered to determine whether there is any deterioration in overall scores during the treatment period. Motor deterioration will be assessed from Part 3 of the UPDRS, but total score will also be reported. ***The assessment will be performed during the “ON” phase, approximately 60 minutes after taking levodopa.***
- Improvement in mood as assessed by the Beck Depression Index (BDI-II): The 21-item BDI-II assesses the intensity of depression. Each item is a list of four statements arranged in increasing severity about a particular symptom of depression.

- Improvement in cognition as assessed by the MMSE: The MMSE is an 11-item examination with a score ranging from 0 – 30 with a higher score indicating better memory. The MMSE will be summarized over time.

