
- 1) For this BM the patient responded “No rescue medication used” to the query “Have you used rescue medication within 24 hours prior to this bowel movement?”
- 2) For this BM the patient responded “Yes” to the query “Did you feel like you completely emptied your bowels?”

For the 2nd Cohort of patient:

- 1) No rescue mediation was taken within 24 hours of the Bowel Movement (note: the date and time of the bowel movements and rescue medication (i.e., laxative) use are included in the subjects daily diary data).
- 2) For this BM the patient responded
 - “No” to the query “Do you feel like you have more poop left to pass?”
OR
 - “Yes” to the query “Are you Done for the Day”
OR
 - “Yes” to the query “Did you feel like you completely emptied your bowels?”

CSBM Definition 4:

This is a more stringent definition for CSBMs for Cohort 2, requiring each of the 3 completeness questions to be appropriately answered. A CSBM is a BM which meets each of the following 3 criteria.

For the 1st Cohort of patients:

- 1) For this BM the patient responded “No rescue medication used” to the query “Have you used rescue medication within 24 hours prior to this bowel movement?”
- 2) For this BM the patient responded
 - “Yes” to the query “Did you feel like you completely emptied your bowels?”
OR
 - “No” to the query “Did you feel like you completely emptied your bowels?” but the BSFS Ease of Passage score is 6 or 7.
- 3) The bowel movement has a BSFS Ease of Passage score of 3 or greater (or missing).

For the 2nd Cohort of patient:

- 1) No rescue mediation was taken within 24 hours of the Bowel Movement (note: the date and time of the bowel movements and rescue medication (i.e., laxative) use are included in the subjects daily diary data).
- 2) For this BM the patient met either of these 2 criteria:
 - 2a) The patient responded:
 - “No” to the query “Do you feel like you have more poop left to pass?”
AND
 - “Yes” to the query “Are you Done for the Day”
AND
 - “Yes” to the query “Did you feel like you completely emptied your bowels?”
OR
 - 2b) The BSFS Ease of Passage score is 6 or 7.

3) The bowel movement has a BSFS Ease of Passage score of 3 or greater (or missing).

An SBM is a BM which meets the following criteria:

- For this BM the patient responded “No rescue medication used” to the query “Have you used rescue medication within 24 hours prior to this bowel movement”

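### SBM response can be met by 3 or more SBMs per week although entry caps only CSBMs, so a subject can count as a responder with no change or a decline

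*SAP*

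**What the plan says.** **Response rule.** Protocol 3.2 ("SBM bowel response to ENT-01 during the Fixed Dose period: An SBM bowel response is defined as a weekly SBM rate increase of 1", with an absolute rate of at least 3 as the alternative) and SAP 2.6.2 ("An SBM bowel response is defined as a weekly SBM rate increase of 1 or more compared to baseline or an absolute rate of 3") give the same either/or rule, and both figures are minimum values. Completeness is not part of an SBM: "An SBM is a bowel movement which did not occur within 24 hours after taking rescue medication". Prokinetic response has the same form, with CSBMs in both legs.

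**Entry limits.** All are on complete movements. Inclusion 8 in Protocol 5.3 reads "Self-report of 3 or fewer complete spontaneous bowel movements (CSBMs) per week". Exclusion 3 in Protocol 5.4 removes subjects with "More than 3 complete spontaneous bowel movements per week based upon the average CSBM rate reported during the Screening Period". The eligibility footnote, here from SAP 2.4, reads "Have had <3 CSBMs/week based upon the average CSBM rate during the first 2 screening weeks (baseline period". Total stool frequency appears only in Protocol Appendix 4, as one item of a list from which any two suffice. The Rome IV list in Protocol 5.3 omits it.

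**AND endpoints.** SAP 2.6.3 adds two exploratory endpoints that require both legs. The first uses CSBMs throughout and is explained as a modification of prokinetic response. The second is "A weekly SBM rate increase of 1 or more compared to baseline and an absolute rate of 3 or more CSBMs per week", with no explanation. SAP 4.6.5 names the SAPS-PD improvement as the only categorical exploratory endpoint.

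**Derivation.** SAP 4.6.1 says the two cohorts' diary assessments differ. For cohort 2 CSBMs it finds rescue use from diary dates and times. The SBM rule ("An SBM is a BM which meets the following criteria") then gives one criterion for everyone: the rescue question used for cohort 1 CSBMs.

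**Test.** SAP 4.6.4 uses Fisher's exact test, with CMH by baseline CSBM stratum if numbers allow.

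**The concern.** A responder endpoint should separate subjects who improved from those who did not. Here the absolute leg can already be satisfied before dosing. A sensation of incomplete evacuation is itself a qualifying symptom, so entry can bring in subjects whose SBM rate is well above their CSBM rate. If they stay at or above 3 per week they are responders on either treatment, which pulls the two proportions together. Neither planned test uses baseline SBM rate, so neither repairs this.

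Prokinetic response has a narrower form of the same problem, at a baseline CSBM rate of exactly 3.0.

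Two drafting points add to it. The second AND endpoint in SAP 2.6.3 cannot serve as the stricter form of SBM response while its absolute leg counts CSBMs. And if cohort 2 SBMs and CSBMs follow different rescue rules, a cohort 2 movement could be a CSBM without being an SBM. That would also touch SBM change, time to first SBM, stool consistency and ease of passage, all of which rest on SBMs.

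**Working it through.** The plan gives no response rate, power or baseline figure for SBM response, so there is no stated number to reproduce.

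**1. The definitions side by side.** Take 0 CSBMs and one incomplete, rescue-free movement a day at screening.
- CSBM rate: 0 per week, which breaches no frequency limit.
- SBM rate: 7 × 14 / 14 = 7 per week.
- Fixed Dose period at 3 SBMs per week: change 3 − 7 = −4, so the increase leg fails. The absolute leg is met, and the subject is a responder.

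**2. The boundary at 3.0.** Six CSBMs in 14 days is 7 × 6 / 14 = 3.0 per week. Exclusion 3 and the 1.0–3.0 stratum admit this subject; SAP 2.2 says the stratum was widened to do so. The eligibility footnote (Protocol Table 1 and Appendix 2, SAP 2.4) and Protocol 4.2 and 5.2 require fewer than 3. If admitted, the subject meets the absolute leg of prokinetic response with no change.

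**3. Share already at the threshold (assumed inputs).** Three per week over 14 days means at least 6 SBMs. With a Poisson count of mean 2m, where m is the assumed weekly rate, P(X ≥ 6) is:

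| m per week | 1 | 2 | 3 | 4 | 5 |
|---|---|---|---|---|---|
| Share | 2% | 21% | 55% | 81% | 93% |

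Variation between subjects changes these figures. A gamma-Poisson count with shape 3 gives 26%, 47% and 62% at m = 2, 3 and 4. At m = 4, shapes from 0.5 up to the Poisson limit give 40% to 81%. The only nearby figure in the documents is the phase 2a baseline of 1.2 CSBMs per week (Protocol 2.2), which does not fix the SBM rate.

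**4. Dilution and power.** Let b be the share at or above 3 per week at baseline who stay there. The observed response in each arm is b + (1 − b) × p, with p assumed to be 65% on ENT-01 and 35% on placebo. Evaluable numbers are an assumption built from the planned allocation: (54 + 40) × 0.9 = 84.6 and (18 + 40) × 0.9 = 52.2, taken as 84 and 52. The 10% loss is the rate Protocol 9.2.5 uses in its power calculation. Exact power of Fisher's test, two-sided 0.05:

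| b | ENT-01 | Placebo | Power |
|---|---|---|---|
| 0 | 65.0% | 35.0% | 91% |
| 20% | 72.0% | 48.0% | 78% |
| 45% | 80.8% | 64.3% | 53% |
| 65% | 87.8% | 77.3% | 33% |

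**5. Other assumptions, same pattern.** For cohort 2 alone (40 × 0.9 = 36 per arm), with 80% versus 40% in the other subjects, exact Fisher power is 91%, 74%, 47% and 15% at b = 0, 25%, 50% and 75%.

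**6. What a baseline-aware rule recovers.** High-baseline subjects stay in the denominator and must gain 1 per week. Suppose they make up 45% and respond 40% versus 30% (assumed).
- ENT-01: 0.45 × 0.40 + 0.55 × 0.65 = 53.75%.
- Placebo: 0.45 × 0.30 + 0.55 × 0.35 = 32.75%.
- Power is about 62%, against 53% under the current rule. The full 91% returns only if these subjects respond like the rest.

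**The case against.** The strongest reply is that the consequences are limited. SAP 4.6.3 rests study success on the primary ANCOVA alone. Change in weekly SBM rate is analysed by ANCOVA with its own baseline and is untouched. No multiplicity procedure depends on SBM response, and randomization balances high-baseline subjects in expectation. All of this stands.

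The either/or form also has a history. Phase 2a used the same structure, on CSBMs, as its primary endpoint, so keeping it preserves comparability. An unblinded interim analysis of the first cohort has already been done, so replacing a protocol-defined endpoint now would be a change made with knowledge of data. This stands too, and it argues for adding an analysis and leaving the existing definition in place.

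A reader might infer that many subjects are responders at baseline. The documents do not support that: they give no baseline SBM mean, spread or share, and step 3 runs from 2% to 93%. A reader might also take the AND endpoints as the plan's own safeguard. The SAP never says so. It links only the CSBM version to a secondary endpoint, and the mixed version may be a slip or a deliberate composite.

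The 3.0 case is narrow, and whether such subjects enter depends on passages that disagree. The rescue-rule point may be only drafting, since SAP 2.6.2 defines an SBM the same way for all subjects. The SAP does not say that cohort 2 lacks the rescue question, so it cannot be concluded that cohort 2 SBMs are underivable. What remains is that 4.6.1 gives cohort 2 two different rescue rules.

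**Conclusion.** The point holds as a flaw in a secondary endpoint. Because the absolute leg ignores baseline and entry limits only CSBMs, a subject can be scored an SBM responder with no change or a decline. Prokinetic response shares this at exactly 3.0 CSBMs per week, if such subjects are admitted.

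The size cannot be fixed from the documents. The power losses in step 4 depend on assumed response rates, an assumed evaluable 84:52, and automatic responders who all stay at or above 3 per week. They show direction and scale and are not a forecast.

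Two stronger conclusions do not follow. The rule does not favour ENT-01: it raises response in both arms and shrinks the difference. Nor does the endpoint fail to measure response at all, since for subjects below 3 per week at baseline both legs require some rise.

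The mixed criterion in SAP 2.6.3, the missing entries in 4.6.5 and the two cohort 2 rescue rules in 4.6.1 are separate wording faults that need settling.

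**What to change.** Before final unblinding, and preferably before any unblinded look at cohort 2:

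1. Add to SAP 4.6.4 a pre-specified analysis of SBM and prokinetic response in which the absolute leg counts only when the subject's baseline rate is below 3 per week; others need an increase of at least 1. Report it beside the protocol definition, and record it in SAP section 5, which now states that nothing differs from the protocol.
2. Tabulate baseline SBM rate by arm, including the share at or above 3 per week.
3. In SAP 2.6.3, change CSBMs to SBMs in the SBM AND endpoint, or state that the mixed criterion is intended. List both AND endpoints, with their analysis, in 4.6.5.
4. In SAP 4.6.1, apply the cohort 2 date-and-time rescue rule to cohort 2 SBMs, so that SBMs and CSBMs share one rule.
5. Reconcile the passages that admit a baseline CSBM rate of 3.0 with those that require fewer than 3.

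The cost is SAP wording and one extra table, from data already collected. Responder percentages under the added analysis will be lower in both arms wherever subjects start at or above 3 per week, and the power regained may be modest, as step 6 shows.
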